## Risks

a. Medical risks, listing all procedures, their major and minor risks and expected frequency.

## Experimental Problems

Hemodynamic perturbations are frequent preoperatively. Such events could potentially confound the results of this study if a patient suffers cerebral ischemia from hypotension postoperatively. To adjust for hypotension, patient clinical data will be reviewed daily by research staff, and episodes that meet the criteria for hypotension will be recorded in the case report form. Use of vasoconstrictive or inotropic medications will be recorded. One strength of the protocol is that blood pressure will be measured continuously via the IMx+ software during surgery rather being recorded by an observer.

The use of gadolinium in subjects with renal failure has been implicated in the etiology of a rare condition called nephrogenic systemic fibrosis (NSF). As we state in Magnetic Resonance Imaging, a creatinine level will be measured in all patients before the MRI, and gadolinium will not be given to individuals with an estimated glomerular filtration rate of  $\leq 60$  mL/min or to those needing dialysis after surgery (by FDA and hospital recommendations). Diffusion-weighted MRI will still be performed as part the

assessment of our primary end point. MRA will also be obtained of the head and neck; the neck MRA will be performed with gadolinium in individuals with adequate renal function and without other contraindications for gadolinium, but otherwise will be done without gadolinium. No cases have been reported to the FDA or NSF in individuals with normal renal function or with only mild renal insufficiency. Thus, we do not anticipate an increased risk in our study protocol.

One challenge in this study will be the transport of patients who remain in the postoperative ICU to the MRI scanner, particularly those who require continued mechanical lung ventilation and infusion of vasoactive drugs. The PI or a critical care physician will accompany such patients to the scanner, along with the critical care patient transport team of The Northwestern Memorial Hospital.

AEs will be reviewed by the investigative team at bi-monthly meetings and by the IRB to ensure that these safeguards are adequate to protect the safety of the enrolled patients.

Patients will be excluded if a TCD trans-temporal window cannot be identified before surgery, as the primary intervention is dependent upon detecting the lower CBF autoregulatory threshold using this method. Regardless, monitoring with TCD in surgical patients is challenging for many reasons. Maintaining continuous monitoring is particularly difficult during certain portions of the procedures, such as during tracheal intubation, central venous line placement, transesophageal echocardiography examination, and especially during dissection of the left internal mammary artery, when frequent changes in the patient's body position and the sternal retractor can lead to displacement of the transducers. Intermittent loss of the temporal window during surgery might lead to bias if blood pressure reductions below the autoregulatory threshold are not detected as such. Defining the lower autoregulatory threshold based on mean velocity index or oximetry index should minimize this bias, as the latter will be a continuous measurement not subject to intermittent loss of signal.

Many factors can influence a surgical patient's CBF, including anemia, temperature fluctuations, and volatile (but not intravenous) anesthetics. The effects of many of these variables on CBF autoregulation in this setting have not been examined extensively. Further, the effect of volatile anesthetics on CBF autoregulation is dose dependent. In low to moderate doses, as used clinically, the CBF autoregulatory plateau might be slightly attenuated and minimally shifted to the left. These clinical considerations emphasize the dynamic nature of CBF autoregulation and the need to monitor this parameter continuously when targeting blood pressure management to remain above the point at which CBF is pressure passive. The conditions of this study will enhance the external validity of the findings.

The monitoring of the CBF autoregulatory threshold by a moving linear regression correlation (mean velocity index) requires first ensuring the fidelity of the TCD-derived measurements of middle cerebral artery CBF velocity. Intraoperative TCD monitoring will be performed by individuals with extensive experience in obtaining these measurements,

including in cardiac surgical patients. Our experience is that the demarcation of the lower CBF autoregulatory threshold via mean velocity index is clearly indicated by the error bar graphing, as shown in Figures 3 and 5.

Undergoing an MRI can lead to anxiety in some patients. The investigative team will take measures to reassure the patients during the MRI procedure. Image acquisition will be stopped at frequent intervals to query the patients about distress. A “panic button” will also be available to the patients to notify radiology and study personnel about distress. Some patients may have temporary cardiac pacemaker leads placed after surgery. Coiled pacemaker wires on the surface of the patient could potentially serve as antennae during MRI that might generate heat or induce premature cardiac beats. However, brain MRI will be obtained between postoperative days 1 and 5 or within the first 14 days after the procedure (whatever the patient is more comfortable with), usually after the patient has had the pacemaker wires removed. When necessary, brain MRI can be performed safely in patients with retained metallic materials by taping the pacemaker wires straight to the skin to avoid coiling.

The location and extent of abnormality in perfusion-weighted imaging, diffusion weighted imaging, and conventional MRI are subject to inter-observer discrepancy. However, we have found a high degree of inter-judge reliability in evaluating volume and sites of abnormalities on diffusion-weighted imaging and perfusion-weighted imaging, calculating the number of seconds of delay in perfusion, and determining the affected regions of interest, as described above. We will evaluate effects of cerebral edema on both T2- and perfusion-weighted imaging. Edema is usually significant only in large strokes, is greatest at day 3–10, and is most visible on T2 images. Edema contributes to the hypoperfused region. Patients in whom edema is observed on T2 beyond regions of hypoperfusion on perfusion-weighted imaging will be excluded.

We will obtain only postoperative brain MRI imaging rather than paired pre- and postoperative imaging. The logistics of obtaining preoperative MRI in surgical patients would be a major impediment to recruitment. In some patients, small, clinically undetected diffusion-weighted imaging lesions might result from cardiac catheterization performed before surgery. Such lesions would be mistaken to have occurred during surgery. Therefore, a careful neurologic examination using the NIHSS will be performed before surgery but after cardiac catheterization to ensure that there are no new major deficits. Acute strokes that may have occurred 1–2 weeks before surgery should no longer appear acute at the time of a postoperative DWI MRI (they will no longer be bright on DWI and dark on ADC, as occurs with new strokes).

The significance of new diffusion-weighted imaging lesions to brain regions not involved with higher cerebral function might be debated. However, it is increasingly appreciated that the cumulative impact of a small area of injury on cognitive or other neurologic end points might only be manifest after long-term follow-up. Even if the impact of some diffusion-weighted imaging lesions is minor, development of strategies to improve

neurologic outcomes after cardiac surgery should aim to detect all forms of injury using sensitive means.

The use of 2D TOF MRA in the subset of individuals who cannot receive gadolinium will limit the resolution of this vascular imaging in this subset; however, we anticipate that we should still be able to make global measurements of stenoses. In addition, MRA may suggest stenoses that are not as narrow as they appear, because it measures flow.

Unfortunately, alternative technologies that might give better vascular imaging (such as CT angiography or conventional angiography) expose patients unnecessarily to iodinated dye and, in the case of angiography, an invasive procedure.

Although perfusion-weighted imaging provides an indication of whether a brain area is relatively hypoperfused, it cannot necessarily distinguish whether a brain infarct results from embolism and/or hypoperfusion. Small emboli in well-perfused areas might be transient, but those in areas of hypoperfusion might persist (slow “washout”). In this study, we will count the number of TCD-detected microembolic signals to adjust statistically for the number of emboli in patients with and without diffusion-weighted imaging lesions. Although this study will provide only inferential data on the mechanism of brain injury, the combination of MRI indices and our determination of duration during CPB that mean arterial pressure is below the individual’s CBF autoregulatory threshold, combined with emboli monitoring with TCD, will provide important clinical mechanistic insights.

Failure to obtain study data after a patient is discharged from the hospital (i.e., at the 4- to 6-week postoperative testing sessions) could confound analysis of the secondary cognitive end points of the trial. Multiple reasons might cause patients not to comply with follow-up testing, including death, severe stroke, and discharge to a secondary care facility. Postoperative testing is coordinated to occur during the patient’s postoperative clinic visit with his/her surgeon.

Off-pump CABG surgery is performed in <10% of patients at our institution but is not performed in patients undergoing combined CABG and valve surgery. Although performance of CABG surgery “on-” versus “off-pump” has not been shown to impact neurologic outcomes remarkably based on prospectively randomized trials, it is possible that new data may become available during this trial that might support the decision to perform more surgeries without CPB. Such a decision could conceivably influence recruitment. However, the number of procedures performed at our hospital and the number of patients projected for this study suggest that a sufficient number of patients will be recruited during the planned period of study.

Providing additional information about functional capacity including performance of instrumental ADLs, as well as about ability to drive. This carries minimal additional medical risk to the participant beyond routinely held structured preoperative interview – increased anxiety due to extension of regular pre-operative interview time.

Frailty testing which includes 15 feet walk and performance of hand grip strength. Performance of handgrip strength test using the dynamometer is associated with minimal risks including muscle strain (<1%), discomfort with muscle exertion (~1%), and elevated blood pressure as a response to physical exertion (~5%).

### **Informed Consent**

Before the start of any study-related procedure, a signed and dated IRB-approved informed consent form (ICF) will be obtained and documented in the patient's medical record. The investigator must 1) inform each patient accordingly and allow each patient sufficient time to decide whether or not to participate in the study; 2) give patients and relatives the opportunity to inquire about details of the study and to answer any questions regarding the study; and 3) ensure that the ICF is approved by the IRB when an amendment to the study protocol is made.

A patient is free to withdraw consent for participation in the study at any time, without prejudice to further treatment. Every effort will be made to obtain complete follow-up information on subjects who discontinue from the study prematurely. The reason(s) for a subject's discontinuation must be clearly documented in the subject's medical records and in the case report form (CRF). A patient's participation in the study may be discontinued at any time at the discretion of the PI.

### **Data Management Methods**

Patient information relevant to this study will be recorded on case report forms customized for this study. Only the PI and authorized research staff according to the list of Authorized Study Personnel are entitled to make entries on the case report form. Completed case report forms will be dated and signed by the PI or Sub-PI. Personal patient data will be kept confidential. Case report forms or other documents will identify a patient by initials and study number only. The PI or authorized research personnel will keep the Patient Identification and Enrollment List separately. To allow compliance with GCP principles, each patient will be asked for consent regarding the access to source documents for monitoring, audits, and inspections. The agreement, also covering the use of the data for analyses, must be documented in writing, together with the written ICF for study participation. Data will be transferred from the case report form to a study database (Redcap). This database will include only the patient study number and will be devoid of patient identifying information. All information obtained during the conduct of this study will be regarded as confidential.

### **Quality Assurance**

Before the start of the study, a training session will be conducted to familiarize team members with the protocol and case reporting processes. The protocol and all testing, including the cognitive tools, the NIHSS, and the process for reporting AEs, will be reviewed in detail.

Quality control procedures for the cognitive testing include multilayered training of examiners, review of practice protocols by a board-certified neuropsychologist, and

random selection and review of actual patient testing by a board-certified neuropsychologist during the study period. An initial training session with detailed discussion and demonstration of each test in the battery will be performed led by a member of the research team. All examiners will practice administration of the battery with colleagues. Next, all examiners will practice administration of the battery on three volunteers at the site. The same procedure will be followed if new examiners are added after the study period has begun. During the study period, similar quality control procedures will be in place. Research personnel will be certified for performing the NIHSS using the American Stroke Association's Online NIH Stroke Scale Training Program (<http://asa.trainingcampus.net/uas/modules/trees/windex.aspx>).

All members of the team who assess delirium will undergo rigorous training prior to study enrollment. During the course of the study, team members will meet every two weeks to discuss the diagnosis and evaluation of individual cases of delirium.

### **Data and Safety Monitoring Plan**

At the start of the study, a Data and Safety Monitoring Board (DSMB) will be appointed and will consist of a cardiac surgeon, two neurologist, an anesthesiologist/critical care physician, a statistician ([name]), an independent member from an outside institution and a member from the NIH all with expertise in the area of neurological complications after cardiac surgery. The DSMB members will not be direct participants in the study and they must attest to not having any conflicts of interest with the study or any of its investigators. A team member (TBD) will participate in the DSMB meetings as non-voting member. The DSMB will be charged with oversight of the study's safety and integrity and assessing the risk versus benefits of continuing the study if such questions arise. The DSMB will meet at least bi-annually in person or by conference call or more often, if necessary, based on the progression of the study, including any arising events as communicated by the PI. The DSMB will continue to meet until the completion of the study.

The DSMB will review patient recruitment and patient follow-up, compliance with the protocol including protocol violations, timeliness and completeness of data entry, compliance with patient confidentiality and HIPPA regulations, and communications of adverse events to the IRB. The DSMB members should immediately review the data in order to make any requests for additional information or analysis in a time frame that can allow for such requests to be completed before the scheduled DSMB meeting. Members of the DSMB must maintain confidentiality of the study data until otherwise instructed. An interim analysis of the data looking at safety will be conducted by the DSMB when results from the first 140 subjects are available. If we are given continued funding a meeting of the investigative team will be held to discuss the validity of an additional interim analysis.

### **Plan for reporting unanticipated problems or study deviations.**

#### **Adverse Events**

For this study, an adverse event (AE) is any untoward medical occurrence (e.g., sign, symptom, disease, syndrome, intercurrent illness, or abnormal laboratory finding) that

emerges or worsens relative to baseline during the study periods, regardless of the suspected cause. Untoward medical events that occur from the time the subject signs the ICF to the time of surgery are not considered AEs and should be recorded under medical history. AEs encountered during or after surgery will be recorded on the appropriate AE section of the CRF. All AEs will be evaluated by the PI for their intensity, frequency, relationship to study, and outcome. The intensity of both serious and nonserious AEs will be graded as mild, moderate, or severe. The definitions are as follows: 1) mild, transient event—does not require medical intervention; the normal clinical course for a subject undergoing cardiac surgery is not changed; AND/OR the subject experiences discomfort, but no disruption of normal daily activity; 2) moderate—event may require medical intervention; induces moderate deviation from the normal clinical course for a subject undergoing cardiac surgery; AND/OR the subject experiences sufficient discomfort to reduce or affect normal daily activity; and 3) severe—event requires significant medical intervention and constitutes a marked deviation from the normal clinical course for a subject undergoing cardiac surgery AND/OR the subject is incapacitated and unable to perform normal daily activities.

An AE should be classified as SERIOUS if: 1) it resulted in death (i.e., the AE caused or led to death); 2) it was life threatening (i.e., the AE placed the subject at immediate risk of death); 3) it required or prolonged inpatient hospitalization (i.e., the AE required at least a 24 h inpatient hospitalization or prolonged a hospitalization beyond the expected length of stay); 4) it was disabling (i.e., the AE resulted in a substantial disruption of the patient's ability to carry out normal life functions); or 5) it did not meet any of the serious criteria listed above but potentially jeopardized the patient or required medical or surgical intervention to prevent one of the outcomes listed above. Adverse events will be reported to the IRB, recorded in the study database, and reviewed at the weekly investigators' meeting. Adverse events also will be reviewed at the quarterly Data Safety and Monitoring Board meeting. Serious AEs will be reported to NIH personnel. As soon as the research team notices that an enrolled patient has died or suffered as an adverse event the research team will report it within 24 h and within 72 h respectively.

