## Frailty Assessments:

We will evaluate frailty based on a validated scoring system^1 that characterizes frailty as an age-associated decline in 5 domains: shrinking, weakness, exhaustion, low physical activity, and slowed walking speed.

These measurements are described below based on the original paper.

Each domain will yield a dichotomous score of 0 or 1. We will classify patients scoring 3 to 5 as frail, 1 to 2 as intermediately frail (pre-frail), and 0 as nonfrail. We will also measure the Instrumental Activities of Daily Living scale as part of the frailty assessment. Research staff will undergo frailty screen training to allow consistent measurements of frailty domains in the study population. Frailty assessment will be held in clinic during the patient's preoperative and postoperative visits, and again at the time of the 1 year follow-up visit.

**Weight loss:** "In the last year, have you lost more than 10 pounds unintentionally (i.e., not due to dieting or exercise)?" If yes, then frail for weight loss criterion.

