**Table 4. Grip Strength criteria for frailty**

Gender	Cutoff for grip strength (Kg) criterion for frailty
Men	
BMI ≤ 24	≤ 29
BMI 24.1–26	≤ 30
BMI 26.1–28	≤ 31
BMI > 28	≤ 32
Women	
BMI ≤ 23	≤ 17
BMI 23.1–26	≤ 17.3
BMI 26.1–29	≤ 18
BMI > 29	≤ 21

Instrumental Activities of Daily Living Scale will be used to provide additional information on functional status in the frailty assessment. Seven questions are asked to gauge participant difficulty with using the telephone, walking, preparing meals, managing money, shopping, doing housework, and taking medicines.

Each study subject will participate in the study for approximately 1 year.

Consent will be obtained before any study related events occur. Cognitive and quality of life testing, medical history, TCD measurements (to determine subject eligibility), National Institutes of Health Stroke Scale (NIHSS), ECG and psychomotor testing and Brief Smell Identification Test will be performed within 1- 2 weeks before surgery. We plan to perform this testing in the outpatient center for most patients. Patients who are in-patients prior to surgery will have testing performed on the hospital ward.

On the day of surgery after anesthesia induction the patients will be connected to a transcranial Doppler to monitor middle cerebral artery blood flow velocity and to a near infra-red spectroscopy machine to monitor cerebral oxygenation. Doppler probes are held in place with a fitted head band. The NIRS electrodes will be placed using manufacturer guidelines. Both devices are FDA approved. Transcranial Doppler and NIRS are used to monitor cerebral blood flow autoregulation. Subject randomization will also be done at this time.

Before cardiopulmonary bypass is initiated (after sternotomy and pericardiotomy) the patients will undergo epiaortic ultrasound examination of the ascending aorta to examine for atherosclerotic changes. In many centers epiaortic ultrasound has replaced the traditional palpations by the surgeon of the aorta for the detection of atherosclerosis of the ascending aorta.

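### The adverse event rule files every event between consent and surgery as medical history, including non-fatal harm caused by the study's own preoperative testing

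*Combined protocol and SAP*

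**What the plan says.** The Adverse Events section first defines an AE broadly, as an untoward occurrence that "emerges or worsens relative to baseline during the study periods, regardless of the suspected cause". It then sets a window: "Untoward medical events that occur from the time the subject signs the ICF to the time of surgery are not considered AEs". Those events are to be entered under medical history, while "AEs encountered during or after surgery will be recorded on the appropriate AE section of the CRF". Neither window sentence mentions events caused by a study procedure.

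Consent opens that window before any research activity. The text after Table 4 says "Consent will be obtained before any study related events occur", and the Informed Consent section says the same: "Before the start of any study-related procedure, a signed and dated IRB-approved informed consent form (ICF) will be obtained".

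Research testing then takes place before surgery. The text after Table 4 lists cognitive, quality-of-life and psychomotor testing, the NIH Stroke Scale, the smell test and TCD measurement, all in the one to two weeks beforehand. The Frailty Assessments section adds frailty testing at the preoperative visit ("Frailty assessment will be held in clinic"), and the PRE-OP column of Table 5 agrees. Appendix D describes that session as three timed 15-foot walks and six grip efforts, three with each hand.

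The end of the Experimental Problems section gives risks for the grip test, which it calls minimal: muscle strain below 1%, discomfort about 1% and raised blood pressure about 5%. It also names anxiety from the longer preoperative interview, without a rate.

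**The concern.** Excluding events before surgery from AE tables is normal where the aim is to keep intercurrent illness and the underlying heart disease out of the safety data. This rule also removes harm that the study itself causes. The protocol requires grading, assessment of relationship to study, and reporting for AEs. An event classed as medical history requires none of these.

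At stake is safety oversight of the preoperative testing. The Experimental Problems section says the investigators and the IRB review AEs to check that the safeguards are adequate. They cannot judge the preoperative session from AE data that exclude it by rule. The gap covers any non-fatal event in that window, including one that would meet the protocol's seriousness criteria if it were an AE.

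**Working it through.** The protocol states no figure that depends on this rule, so there is nothing to reproduce. The check is a cross-reading, with a small calculation for scale.

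**Step 1. Does study testing fall inside the excluded window?** The window runs from signature of the consent form to surgery. Consent precedes every study procedure (Informed Consent; text after Table 4). The tests listed above are preoperative (Frailty Assessments; text after Table 4; Table 5). So they fall inside it.

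**Step 2. Does an event in that window have another required route?**

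| Route | Applies to |
|---|---|
| AE section of the case report form | Events during or after surgery |
| Grading and relationship to study (Adverse Events) | AEs |
| IRB, study database, investigators' meeting, scheduled DSMB review (Adverse Events) | AEs |
| NIH (Adverse Events) | Serious AEs |
| 24-hour report of a death (Adverse Events) | Any enrolled patient; not tied to the AE definition |
| Extra DSMB meetings (Data and Safety Monitoring Plan) | Events that the principal investigator chooses to raise |

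A preoperative death would plausibly be caught by the 24-hour clause. For non-fatal harm, the only route left in the table is discretionary.

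**Step 3. Is the same harm treated differently at another session?** Frailty testing is repeated at 4–6 weeks and at 1 year (Table 5). Discomfort from the grip test at either visit occurs after surgery and fits the protocol's mild grade, so it would be an AE. At the preoperative visit it would be medical history.

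**Step 4. Scale.** Inputs: about 150 patients still to enrol (Study Timelines; Number of Local Participants), and the grip-test rates from Experimental Problems. Assumption: each rate applies per patient to one preoperative session. Expected count = N × p; chance of at least one = 1 − (1 − p)^N.

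- Discomfort: 150 × 0.01 = 1.5; chance of at least one = 1 − 0.99^150 = 0.78.
- Strain: below 150 × 0.01 = 1.5; chance of at least one below 0.78.
- Raised blood pressure: 150 × 0.05 = 7.5; chance of at least one = 1 − 0.95^150 = 0.9995.

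None of these would enter the AE section under the present rule. The protocol gives no rate for the walk test and none for serious events.

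**The case against.** The strongest case against the point is that the rule is sensible and the stakes are low. Randomisation follows anaesthesia induction (Patient Randomization), so no preoperative event can result from the allocated strategy, and starting AE collection at surgery keeps the by-arm safety data clean. The named risks are minor, the walk is short and at the patient's usual pace, and harms from the same tests are captured when they are repeated. All of this stands. It justifies leaving out unrelated events, but not leaving out harm caused by a study procedure.

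Four stronger readings are tempting, and the documents do not support them.

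- **That these harms are never reported.** They are documented as medical history, a death is plausibly covered by the 24-hour clause, and the principal investigator may take events to the DSMB. What is missing is a required route for non-fatal harm.
- **That the section contradicts itself.** The phrase about suspected cause belongs to the general AE definition. The exclusion is silent on cause. A specific sentence that narrows a general one can be read without contradiction, so the gap is an omitted exception.
- **That the count should cover the whole trial.** The 280 + 244 = 524 patients enrolled by June 2016 are past any amendment, and the documents do not say how many of them had frailty testing. Only the remaining 150 or so are relevant.
- **That the preoperative session is the riskiest.** No rates by session are given.

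The blood pressure count also needs caution. An expected response to exertion is not necessarily an untoward occurrence, so some of the 7 to 8 might not qualify as AEs at any visit.

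**Conclusion.** The point holds as a minor one. By its stated rule, the protocol classes non-fatal harm from consented preoperative research procedures as medical history, with no required assessment of causality or seriousness and no required report to the IRB, NIH or DSMB.

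This conclusion rests on the wording and not on the counts. The counts assume that the grip-test rates apply per preoperative session and that all of the roughly 150 remaining patients are tested. Leaving out blood pressure rises, they come to 1 to 2 discomfort events and at most 1 to 2 strains. The number of serious events cannot be estimated from the documents. A reader might infer a threat to the trial's results. There is none: no endpoint, sample size or treatment comparison is affected.

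**What to change.** Amend the Adverse Events section along these lines:

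> From consent to the start of surgery, an event judged related to a study procedure (for example frailty testing, cognitive testing or TCD) is recorded as an AE, assessed for seriousness, and reported by the same routes and within the same times as later AEs. Other events in this period are recorded under medical history.

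Relationship is at present assessed only for AEs, so add one question on relationship to a study procedure for untoward events in this window. List the related events separately as pre-randomisation events, outside the by-arm tables.

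The cost is one sentence, one tick box on an existing form and a few extra AE entries. The change helps only patients enrolled after the amendment.
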